#### 9.4.4.3 Outcome

Outcome of AEs will be defined according to the International Council for Harmonisation (ICH) Topic E2B, ICH Guideline, as follows:

- Recovered/Resolved
- Recovered/Resolved with sequelae
- Recovering/Resolving
- Not Recovered/Not Resolved
- Fatal/results in death
- Unknown

#### 9.4.5 Expected Adverse Events

Adverse events reported by 2% or more subjects treated with Saroglitazar Magnesium during the double-blind, active-controlled study with Pioglitazone as the comparator regardless of causality

	Approved by: [name] [name]	Protocol No.: SARO.17.004.02.PROTOCOL Version No.: 2.0
--	------------------------------------	---

 Zydus Discovery DMCC	CLINICAL TRIAL PROTOCOL Saroglitazar Magnesium – Phase 2 SARO.17.004	CONFIDENTIAL Page 66 of 76
--	---	---

included gastritis and asthenia. In the double-blind placebo controlled study, AEs reported by 2% or more subjects treated with Saroglitazar Magnesium included gastritis, dyspepsia, pyrexia and pain. The details of AE(s) experienced during the Saroglitazar studies are mentioned in the IB. Principal Investigator(s) are advised to provide protocol education for patients and caregivers for potential symptoms of adverse effects that should be reported to the site/PI, such as skeletal muscle pain, weight gain, peripheral edema, shortness of breath, hypoglycaemia, etc.

#### **9.4.6 Pregnancy**

[figure not shown]
At the Screening Visit, Visit 6 and Visit 7, every female subject of child-bearing potential will be tested for serum pregnancy test. Urine pregnancy test will be performed at Visit 2, 3, 4 and Visit 5. Women are advised not to become pregnant during the study and for at least 4 weeks  $\pm$  7 days after the end of the treatment period. Adequate contraceptive measures shall be used to prevent pregnancy. Even when contraceptive methods are used, there is a small risk that pregnancy might occur. In case a patient becomes pregnant, then she will be withdrawn from the study and adequate monitoring of the patients will be conducted.

Although pregnancy and lactation are not considered adverse events, it is the responsibility of the PI or their designees to report any pregnancy or lactation in a patient (spontaneously reported to them) that occurs during the study or within 4 weeks of completing the study. All patients who become pregnant must be followed to the completion/termination of the pregnancy. Pregnancy outcomes of spontaneous abortion, missed abortion, benign hydatidiform mole, blighted ovum, fetal death, intrauterine death, miscarriage and stillbirth must be reported as serious events (Important Medical Events). If the pregnancy continues to term, the outcome (health of infant) must also be reported.

The PI or designee should report the pregnancy to Sponsor within 24 hours of being notified. Sponsor will then forward the completed Exposure-in-Utero form to the PI..

#### **9.5 RULES FOR AMENDING PROTOCOL**

All amendments must be documented, dated and signed by all signatories (or their successors) of the original protocol and then will be submitted to Regulatory Authorities/IEC/IRB.

	Approved by: [name] [name]	Protocol No.: SARO.17.004.02.PROTOCOL Version No.: 2.0

 Zydus Discovery DMCC	CLINICAL TRIAL PROTOCOL Saroglitazar Magnesium – Phase 2 SARO.17.004	CONFIDENTIAL Page 67 of 76
--	---	---

Modification only for logistical or administrative changes may be implemented immediately; however, both the IEC/IRB and the Regulatory Authority will be notified.

## 9.6 FINANCIAL DISCLOSURE

The PI and sub-investigator are required to provide financial disclosure information to the Sponsor to permit the Sponsor to fulfil its obligations. In addition, the PI/sub-investigator must commit to promptly update this information if any relevant changes occur during the study and for a period of 1 year after the completion of the study.

## 9.7 DISCONTINUATION OF THE TRIAL BY THE SPONSOR

The Sponsor reserves the right to discontinue this study at any time for failure to meet expected enrollment goals, for safety, or any administrative reasons. The Investigator will be reimbursed for reasonable expenses incurred if it is necessary to terminate the study as per the agreement.

## 9.9 FINAL REPORT AND PUBLICATION POLICY

A report will be prepared under the responsibility of the PI and according to the standards of the Sponsor. It will include the tabulated data and the biostatistical report on the data.

	Approved by: [name] [name]	Protocol No.: SARO.17.004.02.PROTOCOL Version No.: 2.0
---	------------------------------------	---

 Zydus Discovery DMCC	CLINICAL TRIAL PROTOCOL Saroglitazar Magnesium – Phase 2 SARO.17.004	CONFIDENTIAL Page 68 of 76
--	---	---

Zydus Discovery DMCC is, as much as possible, dedicated to support process of free exchange of relevant scientific information. Any publication of the results of this study must be consistent with the ZYDUS publication policy. The rights of the PI and of the Sponsor with regard to publication of the results of this study are described in the Investigator agreement.

## 9.10 ARCHIVING

Subject's files, identification codes and other source data (including original reports of test results, dispensing logs, records of informed consent), IEC/IRB approval letter, correspondence and other documents pertaining to the conduct of the study will be kept as per the SOPs of the institution. No document pertinent to the study shall be destroyed without prior written agreement between the Sponsor and the PI. All documents should be preserved safely after the completion/termination of the study for at least a period of 5 years if it is not possible to maintain the same permanently.

	Approved by: [name] [name]	Protocol No.: SARO.17.004.02.PROTOCOL Version No.: 2.0
---	------------------------------------	---

 Zydus Discovery DMCC	CLINICAL TRIAL PROTOCOL Saroglitazar Magnesium – Phase 2 SARO.17.004	CONFIDENTIAL Page 69 of 76
--	---	---

## 12 APPENDICES

### Appendix 1: List of Known CYP2C8 Inhibitors/Substrates

Selected inducers, inhibitors and substrates of CYP2C8		
Substrates	Inhibitors	Inducers

 
a. Amodiaquinea (antimalarial, anti-inflammatory)
 
b. Cerivastatina (statin)
 
c. Enzalutamide (antiandrogen)
 
d. Paclitaxela(chemotherapeutic)
 
e. Repaglinidea (antidiabetic)
 
f. Torsemidea (loop diuretic)
 
g. Sorafeniba (tyrosine kinase inhibitor)
 
h. Rosiglitazone (antidiabetic) - converted to active metabolitesb
 
i. Buprenorphine (semisynthetic opioid)
 
j. Polyunsaturated fatty acids
 
k. Montelukast (leukotriene receptor antagonist)
 
	
Strong
 
 
a. Gemfibrozila(Hypolipidemic)
 
 
Moderate
 
 
a. Trimethoprima(Antibiotic)
 
 
Unspecified potency
 
 
a. Thiazolidinedionesa(antidiabetic)
 
b. Montelukasta(leukotriene receptor antagonist)
 
c. Quercetina(antiinflammatory)
 
	
Unspecified potency
 
 
a. Rifampicina(Antibiotic)
 

a Flockhart DA (2007). "Drug Interactions: Cytochrome P450 Drug Interaction Table". Indiana University School of Medicine. Retrieved on July 2011
 
b Chapter 26 in: Rod Flower; Humphrey P. Rang; Maureen M. Dale; Ritter, James M. (2007). Rang & Dale's pharmacology. Edinburgh: Churchill Livingstone. ISBN 0-443-06911-5
		

[figure not shown]
Approved by:  
[name] [name]

Protocol No.: SARO.17.004.02.PROTOCOL  
Version No.: 2.0

 Zydus Discovery DMCC	CLINICAL TRIAL PROTOCOL Saroglitazar Magnesium – Phase 2 SARO.17.004	CONFIDENTIAL Page 75 of 76
--	---	---

## Appendix 2: NAFLD Activity Score

[figure not shown]
NAFLD Activity Score		
Item	Definition	Score/Code
Low- to medium-power evaluation of parenchymal involvement by steatosis		
Steatosis	<5%	0
	5% -33%	1
	>33% -66%	2
	>66%	3
Inflammation		
Lobular Inflammation	No foci	0
	<2 foci per 200 X field	1
	2-4 foci per 200 X field	2
	>4 foci per 200 X field	3
Liver cell injury		
Ballooning*	None	0
	Few balloon cells	1
	Many cells/prominent ballooning	2
*Ballooning classification: few indicates rare but definite ballooned hepatocytes as well as case that are diagnostically borderline		
Final NAFLD Activity Score = Steatosis Score + Lobular Inflammation Score + Ballooning Score		
Fibrosis Score		
Item	Definition	Score/Code
Fibrosis Stage	None	0
	Perisinusoidal or periportal	1
	Mild, zone 3, perisinusoidal	1A
	Moderate, zone3, perisinusoidal	1B
	Portal/periportal	1C
	Perisinusoidal and portal/periportal	2
	Bridging fibrosis	3
	Cirrhosis	4
Adapted from: Design and Validation of a Histological Scoring System for Non-alcoholic Fatty Liver Disease. (HEPATOLOGY, Vol. 41, No. 6, 2005 KLEINER ETAL.)		

Approved by: [name] [name]	Protocol No.: SARO.17.004.02.PROTOCOL Version No.: 2.0
------------------------------------	---

**APPENDIX 3: Normal Laboratory Range**

Approved by:  
[name] [name]

Protocol No.: SARO.17.004.02.PROTOCOL  
Version No.: 2.0

1. INTRODUCTION

The purpose of this document is to provide a description of the statistical methods and procedures to be implemented for the analysis of data from SARO.17.004 study. This document is based on protocol version 2.0, dated 02 August 2018. The statistical planning and conduct of analysis of the data from this study will follow the principles defined in relevant International Council for Harmonisation (ICH)-E9 guidelines. This Statistical Analysis Plan (SAP) has been developed prior to database lock or final analysis. Any changes from the planned analysis as described in the protocol are detailed here, and any differences described here supersedes the analysis presented in the protocol. Any deviations from the planned analyses described in this SAP will be documented in the clinical study report, together with the reason for such changes.

Prior to start of any statistical analyses, the database must be authorized and all decisions regarding assignment of patients to study populations must be completed. In addition, protocol deviations must be identified prior to the start of statistical analyses.

2. STUDY OBJECTIVES AND DESIGN

2.1 Study Objectives

Primary Objective

The primary objective of this study is to evaluate the changes in Non-alcoholic Fatty Liver Disease (NAFLD) Activity Score (NAS) at week 24 from baseline and with no worsening of fibrosis in Non-alcoholic Steatohepatitis (NASH) patients.

Secondary Objectives

The secondary efficacy objectives of this study are:

- To evaluate the percentage of responders in the treatment groups.
- To evaluate the percentage of responders, defined as the disappearance of steatohepatitis over the time period up to Week 24 in patients treated with Saroglitazar Magnesium 2 mg and 4 mg.

Document Title:	Statistical Analysis Plan		
Version Number:	1.0	Date:	31 Mar 2020
Protocol Number:	SARO.17.004	Sponsor Name:	Zydus Discovery DMCC

- Changes from baseline to Week 24 in Saroglitazar Magnesium 2 mg and 4 mg for the following parameters:
 - Stage of steatosis, lobular inflammation and ballooning
 - Stage of fibrosis
 - Liver function tests (ALT, AST, ALP, GGT, Direct bilirubin, Total proteins and Albumin).
 - Lipids profile parameters (TG, TC, sdLDL, HDL, LDL, VLDL, non-HDL, ApoA1 and ApoB)
 - Insulin resistance and glycemic control parameters (FPG, HbA1c, Fasting insulin, C-peptide, Adiponectin, HOMA-B and HOMA-IR).
- To assess the safety of Saroglitazar Magnesium 2 mg and 4 mg in patients with non-alcoholic steatohepatitis over 24 weeks of treatment.

2.2 Study Description

[figure not shown]
2.2.1 Study design

This is a Phase 2 randomized, multi-center, double-blind, placebo-controlled proof of concept study to evaluate the safety and efficacy of Saroglitazar magnesium 2 mg and 4 mg in patients with NASH meeting pre-specified inclusion/ exclusion criteria. Male and female patients aged 18 to 75 years will be enrolled in this study. Approximately 15 patients who meet the inclusion and exclusion criteria will be enrolled.

Liver biopsy will be performed at the screening visit to confirm the diagnosis of NASH and to record the baseline NAFLD Activity Score. The histological evidence of NASH is defined as $NAS \geq 4$ with a minimum score of 1 for all of its three components [steatosis, hepatocyte ballooning and lobular inflammation].

This study will be conducted over a period of up to 32 weeks and will include a 4-week screening phase, a 24-week treatment phase and a safety follow-up visit, 4 weeks after the last treatment. The study plan is provided below.

Document Title:	Statistical Analysis Plan		
Version Number:	1.0	Date:	31 Mar 2020
Protocol Number:	SARO.17.004	Sponsor Name:	Zydus Discovery DMCC

[figure not shown]
NOTE: Liver biopsy showing NASH within 6 months preceding Visit 1 can be used.

The study visits are planned at screening [-4 Week (-28 days)], Baseline/Enrollment Visit (Day 1 ± 7 days), Week 6 (Day 43 ± 7 days), Week 12 (Day 85 ± 7 days), Week 18 (Day 127 ± 7 days), Week 24 (Day 169/ ± 7 days) and a safety follow-up visit at Week 28 (Day 197 ± 7 days). All patients will be advised to follow a stable lifestyle. No change in the intensity of lifestyle (Diet/Exercise) will be allowed during the study period.

Document Title:	Statistical Analysis Plan		
Version Number:	1.0	Date:	31 Mar 2020
Protocol Number:	SARO.17.004	Sponsor Name:	Zydus Discovery DMCC

2.2.2 Study plan

Document Title:	Statistical Analysis Plan		
Version Number:	1.0	Date:	31 Mar 2020
Protocol Number:	SARO.17.004	Sponsor Name:	Zydus Discovery DMCC

2.3 Randomization

An independent statistician will generate the randomization schedule(s) for study treatment assignment. Eligible patients will be randomized in a 2:2:1 ratio to receive Saroglitazar 2mg, Saroglitazar 4 mg or placebo. Block randomization will be performed. The block randomization schedule will be generated to ensure the treatment balance by using SAS® software (Version: 9.4 or higher; SAS Institute Inc., USA).

2.4 Blinding and Unblinding

The patients, investigators and all members of the Clinical Study team will be blinded to the treatment assignments while the study is in progress. Furthermore, the randomization scheme will not be available to the clinic staff, study monitors and/or other individuals. All study drug will be supplied in identical packages and study drug kits. The study drug tablets will be similar in color, smell, taste and appearance to maintain adequate blinding of evaluators. Neither the investigator nor the patient should be able to identify the received treatment. Unblinding of the treatment code will be done when all data have been verified, validated and the database is locked.

A sealed copy of the randomization code provided under separate envelope will be retained at the investigational site or as per applicable requirements. If the treatment code needs to be broken in the interest of patient safety, the Investigator is encouraged to contact an appropriate study Sponsor representative prior to unblinding if there is sufficient time. Depend on the individual circumstances (ie, medical emergency), the code may be broken prior to contact with the Sponsor. The study Sponsor must be informed in all cases in which the code was broken and of the circumstances involved. Additionally, the Sponsor may be required to unblind the patient if adverse event meets criteria of a Suspected Unexpected Serious Adverse Reaction (SUSAR) to fulfill expedited regulatory reporting requirements. The event of unblinding will be documented in the source notes.

2.5 Treatments

The following is a list of the study treatment abbreviations and ordering that will be used in the TFLs.

Study Treatment Name	Treatment Abbreviation on TFL	Treatment Order on TFL
Saroglitazar Magnesium 4 mg	Saroglitazar 4 mg	1
Saroglitazar Magnesium 2 mg	Saroglitazar 2 mg	2
Placebo	Placebo	3

Document Title:	Statistical Analysis Plan		
Version Number:	1.0	Date:	31 Mar 2020
Protocol Number:	SARO.17.004	Sponsor Name:	Zydus Discovery DMCC

2.6 Interim Analysis

No interim analysis is planned for this study.

3. ANALYSIS POPULATIONS

Subject evaluability and their impact on analysis populations will be determined prior to locking the database.

3.1 Efficacy Analysis Populations

The modified intent-to-treat (mITT) population includes all randomized patients who receive at least one dose of study drug and have at least one post-baseline visit. The mITT population will serve as the primary population for all efficacy analyses. Last observation carried forward (LOCF) method will be used as an imputation method for the efficacy variables with missing observations.

The supportive analysis of the primary and secondary efficacy endpoints will be conducted using the per-protocol population (PP). The PP population includes all randomized patients who meet all eligibility criteria, completed the study in compliance with the protocol, and do not have any CSR reportable protocol deviation that affects the evaluation of the efficacy endpoints.

The number of patients excluded from mITT and PP populations and a listing of excluded subjects from each analysis population with reason for exclusion will be presented. Any inconsistencies in key study results between mITT and PP populations will be examined and discussed in the clinical study report.

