## 8 BIOSTATISTICS

### 8.1 STATISTICAL DESIGN

Statistical analysis will be performed on efficacy variables.

As this is a proof of concept (PoC) study no formal hypothesis testing will be done. All primary and secondary efficacy analysis will be summarised and analysed, appropriately, for modified Intent-To-Treat (mITT) and Per Protocol (PP) populations. The PP population will consist of all randomized patients completing the treatment phase (has taken  $\geq 80\%$  and  $\leq 120\%$  of the study drug) as per the study protocol and do not have any CSR reportable protocol deviation in such a way that could affect efficacy outcome. The mITT population will consist of all randomized patients who have taken at least one dose of the study treatment and have at least one post-baseline efficacy data. Last observation carried forward method will be used as an imputation method for post-baseline missing values for mITT analysis.

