##### 8.2.1.3 Per-protocol population (PP)

The per-protocol population (PP) includes:

1. All enrolled patients who meet all the eligibility criteria.

	Approved by: [name] [name]	Protocol No.: SARO.17.004.02.PROTOCOL Version No.: 2.0
---	------------------------------------	---

 Zydus Discovery DMCC	CLINICAL TRIAL PROTOCOL Saroglitazar Magnesium – Phase 2 SARO.17.004	CONFIDENTIAL Page 55 of 76
--	---	---

2. Completed the study in compliance with the protocol.
3. Do not have any CSR reportable protocol deviation that affects the evaluation of the efficacy endpoints.

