6.8 Handling of Missing Data

Clarifications, wherever possible, will be obtained from the respective investigator for any missing data or for any illegible entry, unused or unauthenticated data. Subjects are required to have at least one post-baseline visit to be included in the mITT population. Last Observation Carried Forward (LOCF) will be used for the imputation of post-baseline missing values. Baseline values will not be carried forward for the imputation of missing values. Patients discontinued from study will be excluded from the PP population.

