7.3.1 Extent of Exposure

Study duration is defined as the date of last visit minus date of informed consent date plus one. Treatment duration is defined as the date of last dose minus the date of the first dose plus one. If the date of last dose is not available, the date of the last visit will be used in the calculation. If the date of first dose is not available, the date of baseline visit will be used in the calculation. Study duration and the treatment duration will be summarized descriptively.

Treatment compliance is calculated as the total number of tablets taken divided by the expected number of tablets to be taken during the study period multiplied by 100. Treatment compliance will be summarized descriptively. In addition, a categorical summary of compliance will also be presented using the following categories: < 80% 80% to 120% and >120%. A subject's is considered to be compliant, if he/she takes 80% to 120% of the study drug during the study period.

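### The SAP ties the per-protocol set to completing the study, which runs to the off-drug Week 28 visit, so a patient with complete Week 24 efficacy data who is lost before Visit 7 drops out of it

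*SAP*

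**What the plan says.** The documents word the PP set in two ways.

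- **Study completion.** SAP 3.1 admits randomized patients who meet all eligibility criteria and "completed the study in compliance with the protocol, and do not have any CSR reportable protocol deviation" bearing on efficacy evaluation. SAP 6.8 adds: "Patients discontinued from study will be excluded from the PP population". Protocol 8.2.1.3 has the same criterion ("Completed the study in compliance with the protocol"), and protocol 8.2.6 also removes patients discontinued from the study.
- **Treatment completion.** Protocol 8.1 reads: "The PP population will consist of all randomized patients completing the treatment phase". It defines this in a parenthesis as having taken 80-120% of study drug.

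SAP section 1 says that where the SAP differs from the protocol's analysis, the SAP prevails. The study-completion wording therefore governs.

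SAP 2.2.1 describes a study of up to 32 weeks made up of screening, "a 24-week treatment phase and a safety follow-up visit, 4 weeks after the last treatment". Protocol 7.2 lists only safety procedures at Visit 7 (Week 28). SAP 6.2 sets every efficacy endpoint at Week 24. Protocol 4.5 names loss to follow-up as a reason for discontinuation from the study, with no Week 24 cut-off.

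The 80-120% limit appears in the SAP only under exposure (7.3.1), where compliance is "the total number of tablets taken divided by the expected number of tablets to be taken during the study period", times 100. It is not linked to PP membership.

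**The concern.** A PP set should hold the patients whose efficacy data reflect treatment as planned. Tying it to study completion makes membership depend on a visit that contributes no efficacy endpoint. A patient can take all tablets, have the Week 24 biopsy and bloods, and still leave PP through being lost in the four weeks that follow.

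PP is the only sensitivity analysis in the SAP (6.5), and SAP 3.1 commits the study report to discussing inconsistencies between mITT and PP. For NAS the visit schedule has one post-baseline biopsy, at Visit 6, and SAP 6.8 does not carry baseline forward. LOCF can therefore change little, and the mITT/PP contrast rests mainly on who is admitted to PP. With arms of 6, 6 and 3, one patient can create or hide an apparent inconsistency.

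**Working it through.** **Figures in the documents**

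- Study length (SAP 2.2.1): 4 + 24 + 4 = 32 weeks, which reproduces the stated 32. The follow-up visit is needed to reach it.
- Visit 7 against Visit 6 (protocol 7.1): (197 - 169)/7 = 4 weeks after the Week 24 visit.
- Allocation (SAP 4): 15 x 2/5, 15 x 2/5 and 15 x 1/5 give 6, 6 and 3, as stated.

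**Applying the rules to two patients, both fully dosed with a Week 24 biopsy**

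1. *Lost to follow-up after Week 24.* Protocol 4.5 counts this as discontinuation from the study. SAP 6.8 then excludes the patient from PP. Under protocol 8.1 the same patient qualifies, if otherwise compliant.
2. *Misses Visit 7 only.* The deviation criterion does not remove this patient, because it covers only deviations that affect evaluation of efficacy. Exclusion turns on whether the study was completed, and neither document defines that.

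**Size of one exclusion**

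- Share of arm: 1/3 = 33% on placebo; 1/6 = 17% on either dose.
- Smallest attainable two-sided Fisher p, active against placebo, for the responder endpoints: 1/84 = 0.012 with 6 v 3, and 1/28 = 0.036 with 6 v 2.
- Half-width of the 95% CI for a difference in mean change, in SD units, is t x sqrt(1/n1 + 1/n2). It is 1.67 with 6 v 3 (7 df) and 2.00 with 6 v 2 (6 df).
- The documents give no rate of loss between Week 24 and Week 28. If it is assumed to be 5%, 10% or 20%, the chance that at least one of 3 placebo patients is lost, 1 - (1 - q)^3, is 14%, 27% or 49%. The expected loss among 15 is 0.75, 1.5 or 3 patients.

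**Secondary point: the compliance limit**

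SAP 7.3.1 does not fix the expected number of tablets. Assume one a day for 24 weeks, or 168.

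- 0.80 x 168 = 134.4, so 135 tablets are needed (135/168 = 80.4%).
- 168 - 135 = 33 final daily doses (4.7 weeks) can be missed with compliance still at or above 80%. Dosing could end at 135/7 = week 19.3.
- If expected tablets follow the actual Visit 6 date (161 to 175), the minimum is 129 to 140 tablets, and 32 to 35 final doses can be missed.
- Longer gaps fail the limit: stopping at Week 18 gives 126/168 = 75%, and at Week 12 gives 84/168 = 50%. Compliance below 80% is a listed deviation in protocol 7.5.

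**The case against.** **Little depends on PP.** mITT is the primary efficacy set, there is no formal testing, and p-values are descriptive. A patient lost after Week 24 stays in mITT with their own biopsy, and SAP 3.1 requires a listing of PP exclusions with reasons. All of this stands and limits the importance of the point.

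**The SAP did not introduce the wording.** SAP 3.1 and 6.8 follow protocol 8.2.1.3 and 8.2.6. That is right: the conflict lies within the protocol, and the SAP resolves it towards study completion.

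**Stronger readings that the documents do not support**

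- *Everyone who misses Visit 7 is dropped.* This is firm only for a patient who is discontinued from the study, for example through loss to follow-up. For a missed visit alone it depends on an undefined phrase.
- *Tying PP to study completion lets early drug stoppers in.* The tolerance comes from the 80% limit, and protocol 8.1 carries the same limit in its parenthesis. SAP 3.1 also requires compliance with the protocol, and protocol 5.2 specifies daily dosing for 24 weeks. Protocol 4.4 treats some treated patients as not completing the study according to protocol, and protocol 7.5 allows persistent dosing non-compliance to become reportable. These texts may already exclude an early stopper. What remains is that SAP 6.8 names discontinuation from the study but not from study drug, and that protocol 4.5 and 4.6 foresee continued follow-up after drug is stopped.
- *A fixed interval between last dose and biopsy.* Holding 168 tablets fixed and moving Visit 6 over Days 162-176 gives 27 to 41 days from a last dose on Day 135. Letting expected tablets follow the visit gives 33 to 36 days (162 - 129; 176 - 140). Protocol 4.4 also provides for an end-of-treatment biopsy after at least 12 weeks of treatment, so the interval could be shorter. None of these figures is set by the plan.

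**Conclusion.** The point holds in limited form. Under the stated rules, a patient with full dosing and complete Week 24 efficacy data who is lost to follow-up before Visit 7 leaves PP, although no efficacy endpoint is set after Week 24. Protocol 8.1 would keep that patient. The cost is a third of the placebo arm or a sixth of an active arm per patient. How often it would happen is unknown, and the rates used above are assumptions.

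Two parts are less firm. Exclusion for a missed Visit 7 alone is the natural reading, not a certainty. A patient who stopped about 33 days before Week 24 could arguably still count as compliant, but this assumes 168 expected tablets and that the general requirement of protocol compliance does not already exclude such a patient.

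The effect is confined to a supportive, descriptive analysis. It deserves correction before database lock because the remedy is simple and the arms are very small.

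**What to change.** Reconcile SAP 3.1 and 6.8 with protocol 8.1, 8.2.1.3 and 8.2.6, so that one definition applies:

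- PP requires eligibility, completion of the 24-week treatment phase through Visit 6, 80-120% of expected tablets, and no reportable deviation that affects efficacy evaluation.
- State the denominator, for example tablets due from first dose to the Visit 6 date, or a fixed 168.
- State that attendance at Visit 7 is not required.
- In SAP 6.8, exclude from PP those who discontinued study drug or the study before the Week 24 visit.
- Require the Week 24 biopsy only for the histology endpoints. Making it a condition of all PP membership would remove compliant patients without a biopsy from the liver-test, lipid and glycaemic analyses, which again loses valid Week 24 data.

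The change affects analysis text only, uses dose and visit dates that SAP 7.3.1 already relies on, and alters no trial procedure. It costs slightly more bookkeeping, because PP membership may differ by endpoint. It also explicitly removes early drug stoppers from a supportive analysis, which may make that set smaller.
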